APPENDIX XV: FOLLOW-UP PARTICIPANT QUESTIONNAIRE

Screening HIV-Infected Women for Anal Cancer Precursors

FOLLOW-UP QUESTIONNAIRE FOR VISITS 2-5.

Participant ID: 084 - _____ - _____

Date of administration: ____ / ____ / ____ - ____

Administered by: _____

[figure not shown]
Location of administration (e.g., clinic or telephone): _____

Thank you for agreeing to speak with me today.

I will be asking some personal questions—most of them are the same or similar to the original questions you answered 6 months ago. Again, if you feel uncomfortable answering any question or want to stop at any time, just let me know.

CURRENT HEALTH STATUS (EQ-5D-5L)

**The best health
you can imagine**

**The worst health
you can imagine**

1. To begin, I will ask some general health questions.

- We would like to know how good or bad your health is TODAY.
- This scale is numbered from 0 to 100.
- 100 means the best health you can imagine.
- 0 means the worst health you can imagine.
- Mark an X one the scale to indicate how your health is TODAY.
- Now, please write the number you marked on the scale in the box below.

YOUR HEALTH TODAY =

Please tell me which one of these statements best describes your health today (repeat for each section). Under each heading, please tock the ONE box that best describes your health TODAY.

2. MOBILITY:

| | |
|---------------------------------------------------|----------------------------|
| I have no problems in walking about. | 1  |
| I have slight problems in walking about. | 2  |
| I have moderate problems in walking about. | 3  |
| I have severe problems in walking about. | 4  |
| I am unable to walk about. | 5  |

3. SELF-CARE:

| | |
|-------------------------------------------------------------|----------------------------|
| I have no problems washing or dressing myself. | 1  |
| I have slight problems washing or dressing myself. | 2  |
| I have moderate problems washing or dressing myself. | 3  |
| I have severe problems washing or dressing myself. | 4  |
| I am unable to wash or dress myself. | 5  |

4. USUAL ACTIVITIES (e.g., work, study, housework, family, or leisure activities):

| | |
|------------------------------------------------------------|----------------------------|
| I have no problems doing my usual activities. | 1  |
| I have slight problems doing my usual activities. | 2  |
| I have moderate problems doing my usual activities. | 3  |
| I have severe problems doing my usual activities. | 4  |
| I am unable to do my usual activities. | 5  |

5. PAIN/ DISCOMFORT:

| | |
|--------------------------------------------|----------------------------|
| I have no pain or discomfort. | 1  |
| I have slight pain or discomfort. | 2  |
| I have moderate pain or discomfort. | 3  |
| I have severe pain or discomfort. | 4  |
| I have extreme pain or discomfort. | 5  |

6. ANXIETY/ DEPRESSION:

| | |
|----------------------------------------------|----------------------------|
| I am not anxious or depressed. | 1  |
| I am slightly anxious or depressed. | 2  |
| I am moderately anxious or depressed. | 3  |
| I am severely anxious or depressed. | 4  |
| I am extremely anxious or depressed. | 5  |

ANXIETY AND DEPRESSION [PHQ-4]

The following answer choices are: “not at all”; “several days”; “more days than not”; “nearly every day”; and “don’t know”.

7. Over the past 2 weeks have you been bothered by these problems?

| | Not at all | Several days | More days than not | Nearly every day | Don't know |
|----------------------------------------------------|-------------------|---------------------|---------------------------|-------------------------|-------------------|
| Feeling nervous, anxious, or on edge | 0 | 1 | 2 | 3 | 98 |
| Not being able to stop or control worrying | 0 | 1 | 2 | 3 | 98 |
| Feeling down, depressed, or hopeless | 0 | 1 | 2 | 3 | 98 |
| Little interest or pleasure in doing things | 0 | 1 | 2 | 3 | 98 |

SEXUAL BEHAVIORS AND SEXUAL HISTORY

Contact during sex is an important way in which some women get abnormalities on the cervix and anus. We need your help in understanding how women's behavior can affect their health. For this reason, it is very important for you to answer some questions about your personal sexual behavior. Each question will specify the type of sex to which we refer. Please consider any sexual experiences, even sex that was upsetting or involuntary such as rape.

We assure you that your answers will be kept confidential. By providing this information, you will help us a great deal with this study.

Please listen to each question carefully and answer as honestly as possible, even if you only had that type of sexual experience one time.

8. Have you experienced sexual assault in the past 6 months?

| Response | Code |
|-------------------|-------------|
| Yes | 1 |
| No | 2 |
| I don't know | 98 |
| Decline to answer | 99 |

Sex with Men

The next questions refer only to vaginal sex with men. This is when a man puts his penis, fingers or a sex toy/object in a woman's vagina.

9. Have you had vaginal sex with a man in the past 6 months?

| No (skip to question 12) | Yes | Decline to answer (skip to question 12) |
|------------------------------------|------------|---------------------------------------------------|
| 0 | 1 | 99 |

10. How many men have you had vaginal sex with **in the past 6 months**?

| None | 1 | 2-5 | 6-10 | More than 10 | Unsure | Decline to answer |
|------|---|-----|------|--------------|--------|-------------------|
| 0 | 1 | 2 | 3 | 4 | 98 | 99 |

11. How often were condoms used to cover the man's penis, sex toy or object when you had vaginal sex with a man in the past 6 months?

| Never | Rarely | Sometime s but less than half | About half the time | More than half the time | Every time | Unsure | Decline to answer |
|-------|--------|-------------------------------|---------------------|-------------------------|------------|--------|-------------------|
| 0 | 1 | 2 | 3 | 4 | 5 | 98 | 99 |

Now I am going to ask you questions about anal sex with a man. This is when a man puts his penis, finger, sex toy or object in your anus.

12. Have you had anal sex with a man in the past 6 months?

| No (skip to question 17) | Yes | Decline to answer (skip to question 17) |
|-----------------------------|-----|--------------------------------------------|
| 0 | 1 | 99 |

13. When was the last time a man put his penis in your anus?

| Within the past week | Within the past month | Within the past 6 months | Unsure | Decline to answer |
|----------------------|-----------------------|--------------------------|--------|-------------------|
| 1 | 2 | 3 | 98 | 99 |

14. How many men have you had anal sex with **in the past 6 months**?

| None | 1 | 2-5 | 6-10 | More than 10 | Unsure | Decline to answer |
|------|---|-----|------|--------------|--------|-------------------|
| 0 | 1 | 2 | 3 | 4 | 98 | 99 |

15. How often did you have anal sex with a man **in the past 6 months**?

| Never | Less than 1 time/month | 1-3 times/month | Once/week | 2-6 times/week | Daily | Unsure | Decline to answer |
|-------|------------------------|-----------------|-----------|----------------|-------|--------|-------------------|
| 0 | 1 | 2 | 3 | 4 | 5 | 98 | 99 |

16. How often was a condom used to cover the man's penis, finger, sex toy or object when you had anal sex with a man **in the past 6 months**?

| Never | Rarely | Sometimes but less than half | About half the time | More than half the time | Every time | Unsure | Decline to answer |
|-------|--------|------------------------------|---------------------|-------------------------|------------|--------|-------------------|
| 0 | 1 | 2 | 3 | 4 | 5 | 98 | 99 |

SEXUALLY TRANSMITTED INFECTIONS

The following questions ask about infections and diseases that are sexually transmitted. Once again, I assure you that your answers will be kept confidential.

Please let us know if, in the past 6 months, you have been diagnosed with or treated for any of the infections we ask about now.

17. Have you had anal warts in the past 6 months? These are **warts** inside or around your anus.

| No | Yes, in the past 6 months | Unsure/Don't know | Decline to answer |
|----|---------------------------|-------------------|-------------------|
| 0 | 1 | 98 | 99 |

18. Have you had warts inside your vagina, on the vulva, or in both places in the past 6 months?

| No | Inside | Outside | Both | Unsure | Decline to answer |
|----|--------|---------|------|--------|-------------------|
| 0 | 1 | 2 | 3 | 98 | 99 |

19. Have you had **herpes** around the vagina or anus in the past 6 months? These are painful blistering sores around your private parts.

| No | Yes, in the past 6 months | Unsure/Don't know | Decline to answer |
|----|---------------------------|-------------------|-------------------|
| 0 | 1 | 98 | 99 |

20. Have you had **Chlamydia in the past 6 months**? This is an infection transmitted during sexual contact.

| No | Yes, in the past 6 months | Unsure/Don't know | Decline to answer |
|----|---------------------------|-------------------|-------------------|
| 0 | 1 | 98 | 99 |

21. Have you had **Gonorrhea (“clap” in the past 6 months**? This is an infection transmitted during sexual contact.

| No | Yes, in the past 6 months | Unsure/Don't know | Decline to answer |
|----|---------------------------|-------------------|-------------------|
| 0 | 1 | 98 | 99 |

22. Have you had **pelvic inflammatory disease (PID) or infection of your fallopian tubes or ovaries in the past 6 months?**

| No | Yes in the past 6 months | Unsure/ Don't know | Decline to answer |
|----|--------------------------|-----------------------|-------------------|
| 0 | 1 | 98 | 99 |

23. Have you had **syphilis in the past 6 months?** This is an infection transmitted during sexual contact. (The treatment is weekly painful penicillin shots.)

| No | Yes in the past 6 months | Unsure/ Don't know | Decline to answer |
|----|--------------------------|-----------------------|-------------------|
| 0 | 1 | 98 | 99 |

PRE-PROCEDURE EXPLANATION AND QUESTIONS [Acceptability]

In addition to the previous questions, you have consented to have some procedures done today for this study. These procedures are an anal Pap smear, high resolution anoscopy and a biopsy of any abnormal tissue or area that is seen.

Please tell me if you have any of the following concerns about having the following examinations or procedures. For each of these statements, please tell me whether you **agree** or **disagree**. Then you will be asked if you slightly or strongly agree/disagree with the statement.

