7.2.2 Exploratory analyses

We will evaluate the acceptability of anal cancer screening based on survey responses regarding participant satisfaction at each study visit ([Appendix XIII](#) and [XV](#)) and phone call surveys ([Appendix XIV](#)) administered after study visits 1, 3,

and 5. Descriptive statistics will be used to characterize participants' acceptability of undergoing anal screening with cytology/HPV and HRA throughout the study to evaluate changes in perceptions. Generalized estimating equations (GEE) will be used to assess acceptability over time adjusting for intrapatient variability. Acceptability will be correlated with clinical and behavioral risk factors, e.g., history of sexual assault, depression, anxiety, medication compliance, sexual behaviors using GEE methods.

A fully de-identified dataset from the study, which will include data obtained on quality of life, anxiety, costs, and procedures, will be made available to [name], MD Anderson, for an economic evaluation of cost effectiveness modeling of anal cancer strategies in HIV-positive women.

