APPENDIX IV: HIGH RESOLUTION ANOSCOPY (HRA) AND ANAL BIOPSIES

Procedure for performing HRA

High resolution anoscopy should only be done **after** the specimens for anal cytology and HPV testing are collected. The patient will already be positioned for anal evaluation. A mixture of a topical anesthetic (e.g., 2% lidocaine jelly or EMLA ointment) and water-soluble lubricating jelly should be used as a lubricant. A digital anal/rectal exam should be performed noting any masses or areas of induration. The procedure for HRA is as follows:

- 1) Insert the plastic disposable anoscope, remove obturator, and place a cotton swab wrapped in gauze soaked in 3-5% acetic acid into anus.
- 2) Remove the anoscope over the swab and leave in place for 1 to 2 minutes.
- 3) Remove the swab and re-insert the anoscope. Carefully examine the anal canal with a colposcope.
- 4) Re-apply acetic acid as necessary to ensure adequate detection of lesions.
- 5) If acetowhiteness is noted, note vascular characteristics, if present.
- 6) Lugol's solution (iodine) may be used to aid identification of possible AIN near the squamocolumnar junction.
- 7) Biopsy up to six of the most abnormal appearing areas (directed biopsies) clinically suspicious for AIN. Local anesthetic (e.g., 1% lidocaine with or without epinephrine or .5% bupivacaine) may be used at the provider's discretion prior to biopsy.
- 8) Each study participant will have *at least* two biopsies. If fewer than two directed biopsies are taken from two different quadrants, then random biopsy/biopsies will be done such that there will be *at least* two biopsies from *at least* two different quadrants.
- 9) Attain hemostasis prior to removal of the anoscope (with pressure, Monsel's solution, or silver nitrate).
- 10) An external genital exam should be performed to note the presence of condyloma and other abnormalities.
- 11) Apply acetic acid to perianal area and examine carefully with colposcope.
- 12) Biopsy any external (perianal) areas clinically suspicious for AIN, using a local anesthetic (e.g., 1% lidocaine with or without epinephrine or .5% bupivacaine) prior to biopsy.
- 13) Participants with signs or symptoms consistent proctitis or sexually transmitted infections other than HPV should be referred for appropriate diagnosis and treatment.

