PRE-PROCEDURE EXPLANATION AND QUESTIONS [Acceptability]

In addition to the previous questions, you have consented to have some procedures done today for this study. These procedures are an anal Pap smear, high resolution anoscopy, and a biopsy of any abnormal tissue or area that is seen.

Please tell me if you have any of the following concerns about having the following examinations or procedures. For each of these statements, please tell me whether you **agree** or **disagree**. Then you will be asked if you slightly or strongly agree/disagree with the statement.

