33. HIGH RESOLUTION ANOSCOPY

High resolution anoscopy is done with use of a plastic tube instrument inserted in the anus to look at the tissue under a special light to see if there are warts or other abnormalities in the anal area. Vinegar is used to make any abnormal areas show up better under the light.

Any abnormalities seen will be biopsied, or removed, with a small cutting instrument to send to the laboratory for special analysis.

| Statement | Strongly disagree | Slightly disagree | Neutral | Slightly agree | Strongly agree | Decline to answer |
|-----------------------------------------------|-----------------------------|-----------------------------|---------|-------------------|-------------------|----------------------|
| I am concerned about pain. | 1 | 2 | 3 | 4 | 5 | 99 |
| I feel the exam will be uncomfortable. | 1 | 2 | 3 | 4 | 5 | 99 |
| I feel at ease. | 1 | 2 | 3 | 4 | 5 | 99 |
| I am prepared to have the procedure. | 1 | 2 | 3 | 4 | 5 | 99 |

34. Which of the following examinations or procedures concerns you the **very most** today? (Choose one)

| Code | Procedure |
|------|--------------------------|
| 0 | No Concern |
| 1 | Anal Pap smear |
| 2 | High resolution anoscopy |
| 3 | Possible biopsy |
| 99 | Decline to answer |

HEALTH BEHAVIOR QUESTIONS

Now I am going to ask you a few questions about yourself.

[from ACTG self report, questions E, H, QL0742(A5257)/ 12-31-08]

35. Are you on HIV medication(s)?

| No (skip to question 37) | Yes | Unsure/Don't know (skip to question 37) |
|-----------------------------|-----|--------------------------------------------|
| 0 | 1 | 98 |

36. Rate your **ability** to take all of your HIV medications as specifically prescribed.

| Very poor | Poor | Fair | Good | Very good | Excellent | N/A | Unsure/Don't know | Decline to answer |
|-----------|------|------|------|-----------|-----------|-----|-------------------|-------------------|
| 1 | 2 | 3 | 4 | 5 | 6 | 97 | 98 | 99 |

SMOKING QUESTIONS

37. Altogether, have you smoked at least 100 or more cigarettes in your entire lifetime?

INTERVIEWER NOTE: IF NECESSARY: 5 packs = 100 cigarettes

| No (skip to question 40) | Yes | Unsure/Don't know (skip to question 40) | Decline to answer |
|-----------------------------|-----|--------------------------------------------|-------------------|
| 0 | 1 | 98 | 99 |

Ask former and current smokers the following questions:

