24. ANAL PAP SMEAR

[OPTIONAL EXPLANATION: An anal Pap smear will be taken. This is like a cervical Pap smear. A Q-tip type swab will be inserted into the anus by the doctor or nurse practitioner to obtain cells that will be sent to the laboratory to check for abnormalities.]

| Statement | Strongly disagree | Slightly disagree | Neutral | Slightly agree | Strongly agree | Decline to answer |
|----------------------------------------|-----------------------------|-----------------------------|---------|--------------------------|--------------------------|-------------------|
| I am concerned about pain. | 1 | 2 | 3 | 4 | 5 | 99 |
| I feel the exam will be uncomfortable. | 1 | 2 | 3 | 4 | 5 | 99 |
| I feel at ease. | 1 | 2 | 3 | 4 | 5 | 99 |
| I am prepared to have the procedure. | 1 | 2 | 3 | 4 | 5 | 99 |

25. ONLY FOR VISITS 3 AND 5

HIGH RESOLUTION ANOSCOPY

[OPTIONAL EXPLANATION: High resolution anoscopy is done with use of a plastic tube instrument inserted in the anus to look at the tissue under a special light to see if there are warts or other abnormalities in the anal area. Vinegar is used to make any abnormal areas show up better under the light.]

Any abnormalities seen will be biopsied, or removed, with a small cutting instrument (after more numbing medication is injected) to send to the laboratory for special analysis.]

| Statement | Strongly disagree | Slightly disagree | Neutral | Slightly agree | Strongly agree | Decline to answer |
|----------------------------------------|-----------------------------|-----------------------------|---------|-------------------|-------------------|----------------------|
| I am concerned about pain. | 1 | 2 | 3 | 4 | 5 | 99 |
| I feel the exam will be uncomfortable. | 1 | 2 | 3 | 4 | 5 | 99 |
| I feel at ease. | 1 | 2 | 3 | 4 | 5 | 99 |
| I am prepared to have the procedure. | 1 | 2 | 3 | 4 | 5 | 99 |

26. Which of the following examinations or procedures concerns you the **very most** today? (Choose one)

FOR VISITS 3 AND 5

| Code | Procedure |
|------|--------------------------|
| 0 | No concern |
| 1 | Anal Pap smear |
| 2 | High resolution anoscopy |
| 3 | Biopsy |
| 99 | Decline to answer |

FOR VISITS 2 AND 4

| Code | Procedure |
|------|-------------------|
| 0 | No concern |
| 1 | Anal Pap smear |
| 99 | Decline to answer |

HEALTH BEHAVIOR QUESTIONS

Now I am going to ask you a few questions about yourself.

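### The follow-up questionnaire announces HRA and biopsy at Visits 2 and 4, where neither is scheduled, and its script differs from Visit 1, so Visit 1 versus follow-up change in the pre-procedure acceptability items cannot be separated from wording

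*Combined protocol and SAP*

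**What the plan says.** Section 7.2.2 (exploratory analyses) plans descriptive statistics on how acceptable women find "undergoing anal screening with cytology/HPV and HRA throughout the study to evaluate changes in perceptions", and GEE for acceptability over time. It names two sources: the questionnaires given at each visit (Appendices XIII and XV) and the phone survey after Visits 1, 3 and 5 (Appendix XIV). It mentions no adjustment for differences between forms.

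Appendix XV is headed "FOLLOW-UP QUESTIONNAIRE FOR VISITS 2-5". Its introduction to the acceptability items describes the procedures to be done that day, with no condition on visit: "These procedures are an anal Pap smear, high resolution anoscopy and a biopsy of any abnormal tissue or area that is seen". The Visit 1 form (Appendix XIII) has the same sentence apart from one comma: "These procedures are an anal Pap smear, high resolution anoscopy, and a biopsy of any abnormal tissue or area that is seen".

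Section 4.3.4 and Appendix I schedule HRA with biopsy at Visits 1, 3 and 5 only. The items in Appendix XV respect this: Q25 (HRA) is restricted to Visits 3 and 5, and Q26 has a separate answer list for Visits 2 and 4 that names only the anal Pap.

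The explanations differ between the forms. At Visit 1 (Q32, Q33) they are ordinary script, and the HRA text ends: "Any abnormalities seen will be biopsied, or removed, with a small cutting instrument to send to the laboratory for special analysis". At follow-up (Q24, Q25) they are marked optional, and the HRA text adds "after more numbing medication is injected". The biopsy answer is "Possible biopsy" in Q34 at Visit 1 and an unqualified biopsy in Q26 at Visits 3 and 5. Appendix IV does not vary by visit. Its step 7 says local anaesthetic for directed biopsies "may be used at the provider's discretion", step 8 requires at least two biopsies, and step 12 describes perianal biopsy with local anaesthetic.

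**The concern.** A repeated-measures comparison of perceptions needs the same stimulus each time, or a stimulus that changes only because the day's procedures change. Two departures matter here.

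First, at Visits 2 and 4 a woman rates the anal Pap straight after being told that HRA and biopsy will follow that day. These are the only questionnaire visits without scheduled HRA, so they are where the plan could see how women regard cytology and HPV sampling alone. Appendix XIV gives no substitute, because it is administered only after Visits 1, 3 and 5. Women are also given an incorrect statement about that day's invasive procedures.

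Second, the items on pain, discomfort, ease and preparedness follow a different text at Visit 1 than later. Less concern about pain at Visit 3 could come from experience of the procedure, or from a new phrase about numbing. The plan has no means of telling which.

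**Working it through.** The plan gives no figure on this point. The check sets the scripts side by side and then asks what the GEE can identify.

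**Scripts by visit**

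| Element | Visit 1 | Visits 2 and 4 | Visits 3 and 5 |
|---|---|---|---|
| HRA with biopsy scheduled (Section 4.3.4, Appendix I) | yes | no | yes |
| Introduction announces HRA and biopsy that day | yes | yes | yes |
| Pap explanation | fixed | optional | optional |
| HRA explanation | fixed, no injection | none (item not asked) | optional, injection mentioned |
| Biopsy answer label | qualified as possible | none | unqualified |

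The introduction is constant across visits, so it causes the misdescription at Visits 2 and 4 but not the change of script. The change lies in the explanations and the answer label.

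**Forms affected by the misdescription.** Section 7.1 expects 270 women without HSIL at baseline. With two cytology-only visits each, the maximum is 270 x 2 = 540 forms. Missed visits and later discontinuations lower it.

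**Identifiability.** Let W = 0 for the Visit 1 script and W = 1 for the follow-up script.

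- HRA item (Visits 1, 3, 5): the columns are intercept, Visit 3, Visit 5 and W. Since W = Visit 3 + Visit 5, there are 4 columns of rank 3.
- Pap item (Visits 1 to 5): the columns are intercept, Visits 2, 3, 4, 5 and W. Since W is the sum of the four visit columns, there are 6 columns of rank 5.

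With visit effects in the model, a wording effect and a true change from Visit 1 to follow-up are the same parameter. A straight-line model in time can hold both terms (3 columns, rank 3), but it separates them only by assuming linearity. The correlation of time with W is then 0.87 for the HRA item and 0.71 for the Pap item.

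**Illustration.** Suppose nothing changes except a wording shift of 1 point, and a straight line in months is fitted without W. The slope is the sum of (t - 12)y divided by the sum of (t - 12)².

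- HRA item, t = 0, 12, 24 and y = 0, 1, 1: 12/288 per month, which is 24 x 12/288 = 1.0 point over 24 months.
- Pap item, t = 0, 6, 12, 18, 24 and y = 0, 1, 1, 1, 1: (-6 + 0 + 6 + 12)/360 = 12/360 per month, which is 24 x 12/360 = 0.8 point.

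The 1-point shift is an assumption for scale. The documents give no wording effect, and its true value may be anything from nil upwards. The false trend is proportional to it.

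**The case against.** The strongest reply is that little rests on these items. Acceptability is an exploratory objective with no hypothesis or power claim. Section 7.2.2 also names a second source that no script change touches: the Appendix XIV survey is one fixed form with Pap and HRA ratings, a comparison with the earlier HRA and willingness to repeat it. Visits 3 and 5 share one script. All of this stands, and it limits the point.

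It can also be said that interim HRA is possible. The synopsis provides it for abnormal cytology, and Appendix IX for ASC-H or worse. Both depend on a result and cannot support an unconditional statement about that day. Nor does correct item content in Q24 to Q26 at Visits 2 and 4 undo an introduction just heard.

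Optional re-explanation is defensible for women who have normally had HRA already, and the protocol elsewhere foresees injected anaesthetic (Section 6.1 and Appendix IV, step 12). The brackets in Q25 are irregular, so it is unclear whether the injection phrase falls inside the optional text. If it does, some women hear it and others do not; if not, it is read to all. Either way it is absent at Visit 1.

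A reader might infer three further things that the documents do not support. One is that the introductions' biopsy wording biases change; it is the same on both forms, so it cannot. It may still need reconciling with the two-biopsy minimum in Appendix IV. Another is that anaesthetic use and biopsy counts go unrecorded. The case report forms are not in the documents, Section 4.3 requires clinical information in source documents, and Section 8.4 already reviews the number of biopsies per participant. The third is that a form-version indicator would repair completed data; the rank result above shows that it cannot.

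**Conclusion.** The point holds, with minor severity. The Appendix XV introduction is wrong as written at Visits 2 and 4, and the same form's Q25 and Q26 show it. Separately, the Visit 1 versus follow-up change in the pre-procedure items is fully confounded with the change in explanations and answer label.

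A reader might infer that all change in acceptability is compromised. The documents do not support that: the Appendix XIV survey, Visit 3 versus Visit 5 (apart from whether the optional text was read) and every primary analysis are unaffected.

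The conclusion assumes that the forms are read as printed. It does not depend on the size of a wording effect, which is unknown.

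**What to change.** 1. Make the Appendix XV introduction visit-specific, listing only the procedures scheduled at that visit, with no HRA or biopsy at Visits 2 and 4.
2. At Visits 1, 3 and 5 use the same HRA explanation, the same rule on whether it is read, and the same biopsy answer label.
3. Reconcile the descriptions of anaesthetic and biopsy in both questionnaires with Appendix IV. Which description is right is for the protocol team.
4. For forms completed under the existing scripts, report the Visit 1 versus follow-up change in pre-procedure items as confounded with wording. Base conclusions about change on the Appendix XIV items and on Visit 3 versus Visit 5. State that Pap ratings at Visits 2 and 4 followed an incorrect announcement.
5. Do not add same-visit anaesthetic use or biopsy count to the model for the pre-procedure items. Both arise after the answers are given.

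The cost is a form revision, notification of the IRB and a version break in an exploratory series.
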